#### **7.1.5.1 Laboratory Monitoring**

Participants with laboratory abnormalities consistent with TLS should not receive the scheduled dose. Lab abnormalities consistent with TLS is defined as  $\geq 3$  of following: serum creatinine  $\geq 50\%$  increase, uric acid  $\geq 50\%$  increase, phosphorus  $\geq 50\%$  increase, potassium  $\geq 30\%$  increase, calcium  $\geq 20\%$  decrease, LDH  $\geq 2$ -fold increase prior to dosing should not receive the scheduled dose. Participants with such abnormalities should be re-evaluated again within the next 24 hours (or sooner, if clinically indicated) and then periodically as clinically indicated.

#### **7.1.5.2 Clinical Monitoring**

Inform participants of signs and symptoms that may be indicative of TLS, such as fevers, chills/rigors, dyspnea, nausea, vomiting, muscle tetany, weakness, or cramping, seizures, and decreased urine output. Advise participants to report such symptoms immediately and seek medical attention.

#### **7.1.5.3 Treatment of Tumor Lysis Syndrome**

If TLS occurs, cardiac rhythm, fluid, and serial laboratory monitoring should be instituted. Correct electrolyte abnormalities, monitor renal function and fluid balance, and administer therapeutic and supportive care, including dialysis, as clinically indicated.

A “first-dose effect” has been seen, which is notable for fever, chills, and/or rigors occurring during the evening following the first day of infusion and an increase in creatinine on Day 2, which may be the clinical sequelae of rapid tumor lysis and/or cytokine release. Should a “first dose” effect occur at any point during Cycle 1 or 2, treatment with high dose glucocorticoids (e.g. methylprednisolone 50–100 mg) is recommended. In addition, intravenous fluids, vasopressors, oxygen, bronchodilators, and acetaminophen should be available for immediate use and instituted, as medically indicated.

## **7.2 Pegylated Liposomal Doxorubicin (Doxil® or Lipodox)**

### **7.2.1 Accountability**

Instructions for the receipt, inspection, storage, preparation, administration, and disposal of pegylated liposomal doxorubicin (PLD) are provided in the Pharmacy Manual at each clinical site.

### **7.2.2 Availability**

Pegylated liposomal doxorubicin (PLD) is supplied in 20mg and 50mg vials as a liposomal dispersion at a concentration of 2mg/ml. Vials are intended for single use.

### **7.2.3 Storage and Stability**

Intact vials of pegylated liposomal doxorubicin (PLD) should be stored under refrigeration (2-8°C). Prolonged freezing may adversely affect liposomal drug products, but freezing for less than one month doesn't seem to do so. Pegylated liposomal doxorubicin (PLD) diluted for infusion is stable for 48 hours under refrigeration or 24 hours at room temperature.

### **7.2.4 Preparation**

The desired volume of liposomal dispersion should be withdrawn and must be added to 250ml D5W for IV infusion.

### 7.2.5 Administration

PLD will be administered on Day 8 of each 28-day cycle for a maximum of 6 cycles. PLD dose levels being investigated are: 20mg/m^2, and 30mg/m^2.

Pegylated liposomal doxorubicin (PLD) will be administered as an IV infusion over 1 hour beginning one hour after the beginning of the carfilzomib infusion. On days when carfilzomib is held, PLD should also be held. PLD may be administered through the same line as carfilzomib. Rapid flushing of the infusion line should be avoided post PLD administration.

Pegylated liposomal doxorubicin (PLD) is considered an irritant. This is in contrast to conventional doxorubicin which can cause severe tissue damage on extravasation. Nonetheless, care should be taken to avoid extravasation. If any signs or symptoms of extravasation occur, the infusion should be terminated and restarted in another vein. Apply ice immediately for 30-60 minutes, subsequently alternating on and off every 15 minutes for 24 hours. The extremity should be monitored for 24-48 hours, then the participant may resume normal activity as tolerated. Do not apply heat or sodium bicarbonate. If pain, erythema or swelling persists beyond 48 hours the participant should be referred to a plastic surgeon for possible debridement at the treating physician's discretion.

Infusion-related reactions have been seen in up to 10% of participants per the manufacturer. Participants who experience this reaction generally do so during the first infusion and not with subsequent dosing. Symptoms may include fever, flushing, dyspnea, facial swelling, headache, chills, back pain, tightness in the chest and throat, rash, pruritus, chest pain, hypotension, syncope, sinus tachycardia, apnea, bronchospasm/wheezing, cyanosis, and asthma. Serious and sometimes life-threatening or fatal anaphylactic shock/anaphylactoid reactions have been reported.

Rapid infusion may increase the risk of some infusion-related reactions, and it is suggested that first infusion be initiated at a rate of 1 mg/min. If no reactions are observed after 5-10 minutes, the rate can be increased to complete the infusion over 1 hour.

The dose will be administered at a facility capable of managing hypersensitivity reactions. Medications to treat infusion-related reactions, as well as emergency equipment, should be available for immediate use. If a participant develops a grade  $\geq 2$  infusion-related reaction, the infusion should be stopped and appropriate symptomatic treatment per institutional guidelines should be started immediately. The participant should be observed for at least 30 to 60 minutes depending on the severity of the reaction. At the discretion of the treating physician, treatment may be resumed with administration of H1-blockers and/or steroids. Discontinue treatment if subsequent infusion-related reaction occurs.

Procedures for dose reductions, adjustments and delays are summarized in Section 6.0.

### **7.2.6 Palmar-Plantar Erythrodysesthesia (PPE)**

The onset of PPE is often preceded by exposure of the affected area to friction and/or heat. All participants should therefore be advised to avoid contact with heated objects or bathing and washing with hot water during therapy.

Pyridoxine (vitamin B6) has been reported to decrease the severity of PPE and may decrease its incidence if used in a prophylactic setting. Participants in this study should receive pyridoxine starting on or before Day 1 of Cycle 1 [36, 37] (See section 6.3.2 for details).

Management of PPE once it has appeared is predominantly supportive, with use of treatments such as topical wound care, cold compresses, and elevation. Non-steroidal anti-inflammatory drugs are beneficial in some, and topical 99% dimethyl-sulfoxide has been reported to be of benefit as well, but none of these studies have been studied in a randomized, blinded, prospective fashion. Pyridoxine will be continued in the event that PPE develops despite prophylaxis [38].

## **7.3 Dexamethasone**

### **7.3.1 Accountability**

Dexamethasone is not provided by the study. It will be sourced from a commercial pharmacy.

### **7.3.2 Availability**

Dexamethasone is commercially available in 0.25 mg, 0.5 mg, 0.75 mg, 1 mg, 1.5mg, 4 mg, and 6 mg tablets. It is also available as a 0.5 mg/5mL elixir, and as 4 mg/mL, 10 mg/mL, and 20 mg/mL solution for injection. Please refer to the FDA approved package insert for dexamethasone for product information, extensive preparation instructions, and a comprehensive list of adverse events.

### **7.3.3 Storage and Stability**

Dexamethasone tablets should be stored at room temperature. Solution for injection may be administered diluted in IV fluids over 10-20 minutes.

### **7.3.4 Administration**

Dexamethasone will be administered on the same dosing schedule as carfilzomib

(Days 1, 2, 8, 9, 15, and 16 for 6 cycles and then Days 1, 8, 15, and 22 thereafter until disease progression or clinical relapse). Dexamethasone dose levels being investigated are: 10 mg and 20mg.

Dexamethasone should be taken IV or PO  $\geq$  30 minutes prior to Carfilzomib injection.

After cycle 2, participants enrolled into part 1 of phase 1 (those not receiving dexamethasone) can have dexamethasone 20mg added at the discretion of the treating physician. If dexamethasone is added, the dose modification guidelines (section 6.2) should be followed.

## **7.4 General Concomitant Medication and Supportive Care Guidelines**

### **7.4.1 HSV Prophylaxis**

Acyclovir, or valacyclovir, should be given to all participants, per institutional prophylaxis guidelines, unless contraindicated.

### **7.4.2 Pyridoxine**

It is recommended that all participants be initiated on pyridoxine (vitamin B6) at 200 mg PO QD for prophylaxis against palmar plantar erythrodysesthesia (PPE) starting on or before Day 1 of Cycle 1. Pyridoxine will be continued in the event that PPE develops despite prophylaxis

Vitamin B6 has been reported to cause neuropathy[39]. Therefore any participants who develop a neuropathy more severe than grade 1 while on study should first have this agent discontinued.

### **7.4.3 Glucocorticoids**

Glucocorticoids (other than those required per protocol) are permitted for non-malignant conditions (i.e. asthma, IBD, etc.) but should not be used unless completely necessary. Glucocorticoids have anti-myeloma effect that may lead to confusion of the response data for this study. Glucocorticoid use while on study should be kept minimal.

### **7.4.4 Bisphosphonates**

Participants should receive therapy with bisphosphonates as per institutional guidelines. The choice of agents in this category will be left to the discretion of the treating physicians.

#### **7.4.5 Erythropoietins**

Participants may develop new or worsening anemia and may require either initiation of an erythropoietin preparation or an increased dose of the agent they are already receiving. The choice of preparations to be used will be left to the discretion of the treating physicians.

#### **7.4.6 Filgrastim (G-CSF), Peg-Filgrastim, and Sargramostim (GM-CSF)**

Participants may develop neutropenia and may benefit from initiation of some type of colony stimulating factor, but they should not be given prophylactically. The choice of preparations to be used will be left to the discretion of the treating physicians.

#### **7.4.7 Platelet, RBC, Whole blood, or FFP Transfusions**

Participants may receive platelet, red blood cell (RBC), whole blood, or fresh frozen plasma (FFP) transfusions if clinically indicated.

#### **7.4.8 Antiemetics and Antidiarrheals**

Carfilzomib and PLD treatment can cause nausea, vomiting, or diarrhea, sometimes requiring the use of antiemetics or antidiarrheals, but these agents should not be started prophylactically. If needed, the choice of preparations to be used will be left to the discretion of the treating physicians.

Participants with severe nausea, vomiting, or diarrhea should have fluid and electrolyte replacement administered to prevent dehydration per institutional guidelines.

#### **7.4.9 Palliative Radiation**

Palliative radiation while on study is allowed at the discretion of the treating physician as long as the definition of progressive disease is not met (see section 9.8). Participants meeting the definition of progressive disease should be discontinued from study.

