## 3.0 PARTICIPANT SELECTION

### 3.1 Inclusion Criteria

A participant must meet all of the following criteria to be eligible for enrollment.

- 3.1.1** Histologically confirmed diagnosis of multiple myeloma with a measurable disease parameter at time of screening. A measurable disease parameter is defined as one or more of the following:
- Serum monoclonal protein  $\geq 0.5$  g/dl.
  - 24 hour urine monoclonal protein  $\geq 0.2$  g/24 hour
  - Serum free light chain ratio  $> 5x$  normal ratio with an absolute difference of 10mg/dl between the involved and uninvolved free light chain.
  - Soft tissue plasmacytoma  $\geq 2$  cm measurable by either physical examination and/or applicable radiographs (e.g. MRI, CT, etc).
  - Bone Marrow Plasma Cells  $\geq 30\%$ .
- 3.1.2** Documentation of at least one line of prior myeloma therapy now with relapsed or refractory disease requiring re-treatment.
- 3.1.3**  $\geq 18$  years of age at time of signing the informed consent.

*Note:* No dosing or adverse event data are currently available on the use of carfilzomib in combination with PLD in participants  $< 18$  years of age. Thus, children and adolescents are excluded from this study but will be eligible for future pediatric phase 2 combination trials.

- 3.1.4** Performance status of ECOG  $\leq 2$  or Karnofsky  $\geq 60$  % (see Appendix A and B).

*Note:* Participants with lower performance status based solely on bone pain secondary to multiple myeloma will be eligible.

- 3.1.5** Required Laboratory Values
- ALT (SGPT) and AST (SGOT)  $< 2.5$  x the upper limit of the institutional normal value (ULN).
  - Total bilirubin  $\leq 1.5$  x ULN.
  - ANC  $\geq 1,000$ .
  - Hemoglobin  $\geq 8$  g/dl.
  - Platelets  $\geq 50,000$ .
  - Creatinine clearance  $> 15$  ml/minute using Cockcroft-Gault formula (See Appendix C).
  - For those participants receiving warfarin (Coumadin), unfractionated heparin, or low-molecular weight heparin therapy, the applicable

coagulation parameter that is being monitored must be within the accepted therapeutic ranges for those indications.

*Note:* Transfusions and/or growth factor dependent participants are not excluded if the above parameters can be achieved with such support.

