## **3.2 Exclusion Criteria**

A participant must not meet any of the following criteria to be eligible for enrollment.

- 3.2.1** POEMS syndrome (polyneuropathy, organomegaly, endocrinopathy, monoclonal protein, and skin changes).
- 3.2.2** Plasma Cell Leukemia.
- 3.2.3** Waldenstrom's macroglobulinemia.
- 3.2.4** Pregnant or lactating females.
- 3.2.5** Use of any anti-myeloma drug therapy within 14 days of initiation of study drug treatment excluding corticosteroids if given for an indication other than myeloma.

*Note:* Bisphosphonates are not considered anti-myeloma drugs.

- 3.2.6** Participation in an investigational therapeutic study within 14 days of initiation of study drug treatment.
- 3.2.7** Radiotherapy to multiple sites or immunotherapy within 14 days of initiation of study drug treatment (localized radiotherapy to a single site at least 7 days before start is permissible).
- 3.2.8** Major surgery within 14 days of initiation of study drug treatment.
- 3.2.9** Participants in whom the required program of PO and IV fluid hydration is contraindicated.
- 3.2.10** Prior history of a hypersensitivity reaction to PLD, doxorubicin, bortezomib, carfilzomib, or liposomal drug formulations other than PLD.

History of reactions to liposomal drug formulations other than PLD should be evaluated individually and if their reactions were felt to have been due to the encapsulated agent, rather than the liposomal component itself they should be excluded at the discretion of the investigators.

- 3.2.11** Participants who are known to have active hepatitis A, B, or C viral infection may not participate in this study. Active disease is defined as participants with a known viral hepatitis whose liver function tests are elevated beyond the criteria indicated in Section 3.1.5.
- 3.2.12** Known HIV-seropositive and are taking anti-retrovirals may not participate in this study because of potential interactions between these medications and the investigational agent. Participants who are HIV-seropositive and not on anti-retroviral therapy and who otherwise meet the inclusion/exclusion criteria will be eligible for the study.
- 3.2.13** Compromised cardiovascular function defined as any of the following:
  - EKG evidence of acute ischemia.
  - EKG evidence of medically significant conduction system abnormalities.
  - History of myocardial infarction within the last 6 months.
  - Unstable angina pectoris or cardiac arrhythmia.

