### **9.0 CRITERIA FOR RESPONSE**

#### **9.1 Complete Response**

Complete response (CR) requires all of the following:

- Disappearance monoclonal protein by both protein electrophoresis and immunofixation studies from the blood and urine on at least two determinations, performed a minimum of six weeks apart
- <5% plasma cells in the bone marrow

- Disappearance of soft tissue plasmacytomas for at least six weeks

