## 9.4 Very Good Partial Response

Very good partial response (VGPR) requires all of the following:

- Serum and urine monoclonal protein detectable by immunofixation but not on electrophoresis for at least two determinations, performed a minimum of six weeks apart
- OR
- $\geq 90\%$  reduction in serum monoclonal protein with urine monoclonal protein  $< 100$  mg per 24 hours for at least two determinations, performed a minimum of six weeks apart.
  - If present,  $\geq 50\%$  reduction in the size of soft tissue plasmacytomas (by clinical or radiographic examinations) for at least six weeks.

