## 9.5 Partial Response

Partial response (PR) requires all of the following:

- $\geq 50\%$  reduction in the level of the serum monoclonal protein for at least two determinations performed a minimum of six weeks apart.
- Reduction in urine monoclonal protein by either  $\geq 90\%$  or to  $\leq 200$  mg for at least two determinations performed a minimum of six weeks apart.
- If present,  $\geq 50\%$  reduction in the size of soft tissue plasmacytomas (by clinical or radiographic examinations) for at least six weeks.
- If serum and urine monoclonal protein are unmeasurable, a  $\geq 50\%$  decrease in difference between the involved and uninvolved free light chain levels is required in place of monoclonal protein criteria (The absolute decrease must

- be  $\geq 10$  mg/dl)
- If serum and urine monoclonal protein are unmeasurable and serum free light chain is unmeasurable, a  $\geq 50\%$  reduction in plasma cells is required in place of monoclonal protein provided that baseline bone marrow plasma cell percentage was  $\geq 30\%$

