## 10.0 STUDY CALENDAR

Assessment *	Screening a	Cycles 1 through 6						Cycles 7 and beyond				End of Study b	Follow-up c	
		D1	D2	D8	D9	D15	D16	D1	D8	D15	D22			
Sign informed consent	X													
Medical & treatment history	X													
Vital signs d	X	X	X	X	X	X	X	X	X	X	X	X		
Physical exam e	X	X 						X						
Toxicity assessment	X	X	X	X	X	X	X	X	X	X	X	X	X	
CBC w/ differential	X	X		X		X		X	X	X	X	X	X	
Chemistries f	X	X	X	X	X	X	X	X	X	X	X	X	X	
PT/INR & PTT	X	X 												
SPEP & IFIX g	X	X 				X 		X					X	
24-hour urine total protein, UPEP, & IFIX gh	X	X 				X 		X					X	
Serum free light chains	X	X 				X 		X					X	
Quantitative immunoglobulins (IgA, IgG, IgM)	X	X 				X 		X					X	
Beta-2 microglobulin	X	X 						X					X	
Serum $\beta$ HCG j	X	X						X					X	
EKG & Chest x-ray	X													
MUGA or Echo m	X													
Imaging for plasmacytoma assessment km	X												X 	
Skeletal survey m	X												X 	
Bone marrow biopsy & aspirate n	X												X 	
Correlative samples o	X												X 	
Carfilzomib administration		X	X	X	X	X	X	X	X	X	X	X		
PLD administration				X										
Dexamethasone administration p		X	X	X	X	X	X	X	X	X	X	X		
Follow-up for survival														X

\* All assessments allowed a window of +/- 2 days for scheduling issues (such as holidays)

a: Screening period is D-21 though D1 prior to Carfilzomib dose

b: End of study must be within 30 days of last dose of study drug

c: Follow-up takes place every 3 months for up to 18 months or until resolution or stabilization of adverse events, whichever is longer

d: To be done within 1 hour prior to carfilzomib administration.

e: Physical exam includes height, weight, BSA, performance status, neurological assessment and plasmacytoma assessment if indicated .

f: Chemistries include Complete Metabolic Panel with Renal and Hepatic Panels, LDH, Magnesium, Phosphorous, Uric Acid.

g: SPEP = serum protein electrophoresis, IFIX=immunofixation, UPEP= urine protein electrophoresis.

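### No rule removes an irradiated plasmacytoma from the response assessment, so where a plasmacytoma is the only measurable disease, radiation alone can produce a counted response

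*Combined protocol and SAP*

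**What the plan says.** **Radiation.** Before treatment, Section 3.2.7 excludes recent multi-site radiotherapy, but "localized radiotherapy to a single site at least 7 days before start is permissible". During treatment, Section 7.4.9 says: "Palliative radiation while on study is allowed at the discretion of the treating physician", on condition that progressive disease has not been met. Neither section names plasmacytomas, to include or to except them. Section 7.4.10 bans other anti-myeloma drugs and does not mention radiation.

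**Eligibility.** Section 3.1.1: "A measurable disease parameter is defined as one or more of the following". The list includes a soft tissue plasmacytoma of at least 2 cm, so that lesion can be the sole qualifying disease.

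**Response.** CR (9.1) includes "Disappearance of soft tissue plasmacytomas for at least six weeks". VGPR (9.4) and PR (9.5), where a plasmacytoma is present, ask for a halving: at least 50% "reduction in the size of soft tissue plasmacytomas (by clinical or radiographic examinations) for at least six weeks". None of these items depends on whether the lesion was irradiated. All three categories require their other items too; for example, "Partial response (PR) requires all of the following".

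**Endpoint and records.** Section 15.1 counts confirmed CR, VGPR or PR among all eligible, consented participants who began treatment. In the study calendar, "Screening period is D-21 though D1 prior to Carfilzomib dose". Section 11 lists a radiation history form at baseline only; the per-cycle and off-study lists name no radiation item.

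**The concern.** The phase 2 primary endpoint is a response proportion in a single arm, so there is no control group to absorb the effect of a co-intervention. If a lesion that decides response shrinks because it was irradiated, Section 9 as written records the shrinkage as a response to the three drugs. The protocol accepts this kind of confounding elsewhere: Section 7.4.3 warns that glucocorticoids may muddle the response data and asks for minimal use. Nothing similar is said of radiation. Because no form is named for on-study radiation, the analyst may also be unable to identify the affected participants afterwards.

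**Working it through.** **Step 1: who can be affected.** Apply Section 9 literally to three kinds of participant, each with a plasmacytoma of at least 2 cm that is irradiated and shrinks by at least 50% for six weeks.

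- *A. Plasmacytoma the only measurable disease; serum and urine M-protein visible on immunofixation but not on electrophoresis.* The first M-protein option in 9.4 describes a level, not a change. This participant meets it at entry and continues to meet it if nothing changes. The only item left is the plasmacytoma, so radiation alone gives VGPR.
- *B. Plasmacytoma the only measurable disease; no M-protein; marrow plasma cells below 5%.* 9.5 requires a fall in M-protein, with FLC or marrow of at least 30% as the only substitutes, so PR is not available. 9.4 gives no clear route. Under 9.1, CR is reached if the lesion goes and if M-protein absent throughout is taken to have disappeared. The text does not settle that.
- *C. Response judged on measurable M-protein, or on the FLC or marrow substitute in 9.5.* That criterion must be met as well. Radiation can only turn a plasmacytoma item that would have blocked the response into one that is satisfied.

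**Step 2: when the radiation can fall.**

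- *Before dosing.* Screening opens on Day -21 and radiotherapy is allowed until Day -7, a nominal 21 - 7 = 14 days in which a lesion could be measured and then irradiated. Calendar footnote e puts plasmacytoma assessment, where indicated, in the physical exam. Footnote 1 waives the Cycle 1 Day 1 exam only if screening was within 7 days. A palpable lesion assessed before Day -7 is therefore due for re-examination after any permitted radiotherapy. What remains is mainly lesions seen only on imaging (footnotes k and m require imaging only when clinically indicated) and radiation effect that continues after Day 1. No text says which measurement is the baseline.
- *On study.* The permission ends once PD is met, and 9.8 includes new plasmacytomas and defined growth of existing ones. Lesions that are stable, shrinking or growing below that threshold remain.

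**Step 3: size.** Inputs: null rate 0.20, alternative 0.40 and significance level 0.10 (Section 16). The rule is at least 8 of 24 in Section 16 and at least 6 of 17 in 5.3 (5 or fewer is ineffective). The two sections conflict and must be reconciled, so both rules are shown.

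Formula: P(X ≥ r | n, p) = Σ C(n,i) p^i (1-p)^(n-i), summed from i = r to n.

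The plan's own figure: P(X ≥ 8 | 24, 0.20) = 0.089, with power 0.808 at 0.40. A cutoff of 7 would give 0.189, so 0.10 is a nominal ceiling and not an error. For the other rule, P(X ≥ 6 | 17, 0.20) = 0.106, with power 0.736.

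Now suppose k participants are scored as responders because of radiation and the other n - k respond at 20%. The chance of passing is P(X ≥ r - k | n - k, 0.20):

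| k (assumed) | at least 6 of 17 | at least 8 of 24 |
|---|---|---|
| 0 | 0.106 | 0.089 |
| 1 | 0.202 | 0.160 |
| 2 | 0.352 | 0.267 |
| 3 | 0.552 | 0.414 |

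One such responder, who would otherwise not have responded, adds 1/17 = 5.9 or 1/24 = 4.2 percentage points to the observed proportion. In expectation, the proportion moves from 0.200 to (1 + 0.2 × 16)/17 = 0.247 or (1 + 0.2 × 23)/24 = 0.233.

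**The case against.** The strongest reply is that the gap is narrow, and most of that reply stands.

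- A reader might infer that shrinkage from radiation can pass as a drug response in any participant. The documents do not support that: in kind C the systemic criterion must also be met and confirmed.
- A reader might infer that anyone without M-protein reaches CR once the lesion has gone. That depends on an unsettled reading of 9.1. Kind A does not depend on it.
- A reader might take the whole 14 days before dosing as open. The Cycle 1 Day 1 exam closes part of that window.
- That the radiation is given to a plasmacytoma is an inference from the absence of an exception; the sections speak of a single site and of palliative radiation.
- A reader might expect duration of response to be biased upward. No direction follows: a responder by radiation alone could progress early and shorten it.
- The probabilities for k of 1 or more assume such participants exist. The documents give no frequency.

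A further objection concerns the remedy. If an irradiated lesion were simply scored as failing its item, a participant with a confirmed 90% fall in M-protein would lose the response because of one palliative treatment. That is a fair warning, and the rule has to avoid it.

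The reply does not remove kind A, nor the absence of any text that makes an irradiated lesion not assessable.

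**Conclusion.** The point holds in limited form. As written, Section 9 can assign a counted response to radiation alone when a plasmacytoma is the only measurable disease: clearly through 9.4 with M-protein seen only on immunofixation, and through 9.1 on one reading. Elsewhere radiation can only remove a bar. The number affected is unknown and may be zero. If there is one, the chance of passing at a true 20% rate roughly doubles under the 17-participant rule (0.106 to 0.202) and rises from 0.089 to 0.160 under the 24-participant rule. These figures illustrate sensitivity; they do not estimate the trial's actual error rate. This is a cheap improvement of minor severity.

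**What to change.** Leave the permission for radiation unchanged and add counting rules:

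- **(a) Section 9.** An irradiated plasmacytoma is not assessable. Its shrinkage after radiation earns no response credit, and response is judged on the remaining measurable parameters. A participant with a genuine M-protein response then keeps it.
- **(b) Section 3.1.1 and baseline.** If a lesion is irradiated before dosing, its baseline size is taken after radiotherapy, and it cannot be the sole measurable disease.
- **(c) Section 15.1.** A participant whose only measurable lesion is irradiated on study before a confirmed response counts as a non-responder and stays in the denominator.
- **(d) Section 11.** Record the date and site of on-study radiation on the existing response form.

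The cost is a few sentences and two data fields; re-measurement under (b) arises only for lesions irradiated before dosing. The downside is a possibly slightly lower response rate.
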